This project was funded by the National Institute for Health Research Health Technology Assessment (project number 14/160/01).

The views and opinions expressed therein are those of the authors and do not necessarily reflect those of the HTA, NIHR, NHS or the Department of Health.

an equal probability of being in a treatment or control group. Observational study designs are limited by an inherent imbalance of both known and unknown confounders making some patients more likely to receive surgery than others. As the type of surgery received is not randomly allocated in our study, confounding by indication will be accounted for by using propensity score matching methods. Use of these methods for the assessment of causality in epidemiological studies has been previously described[1]. The propensity score represents the probability that a patient received the intervention (surgery). A logistic equation is fitted where the outcome is surgical intervention versus non-surgical; and any covariates are introduced as potential confounders of subsequent dislocation. We have already identified an expert consensus list of all potential confounders of interest (Appendix E)

Propensity scores are used to match each patient receiving surgery to comparable non-surgical controls using a caliper width of 0.2 standard deviations of the logit of the propensity score[2]. This is a standard method for minimizing confounding by indication, which not only balances observed baseline characteristics in both surgical and non-surgical groups, but also eliminates surgical patients with no comparable controls[3].

Immortal time bias is a common issue in epidemiological studies, where the event of interest cannot occur for a certain time span. In the case of this proposed study immortal time bias would occur due to the definition of exposure, where in the time from first dislocation till receipt of surgery those in the 'surgical arm' cannot have the outcome by design otherwise they would have been classified as non-surgical. To avoid the problem of immortal time bias, we will use time varying exposures, where in a survival analysis the time period previous to the index date of surgery is reclassified as non-surgical for those in the surgical intervention group.

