As in the section above it is vital to deal adequately with confounding by indication. The team of applicants includes academic experts that have been leaders in the development of propensity scoring and prognostic modelling. In randomised controlled trials each person has an equal probability of being in a treatment or control group. Observational study designs are limited by an inherent imbalance of both known and unknown confounders making some patients more likely to receive surgery than others. As the type of surgery received is not randomly allocated in our study, confounding by indication will be accounted for by using propensity score matching methods. Use of these methods for the assessment of causality in epidemiological studies has been previously described[1]. The propensity score represents the probability that a patient received the intervention (surgery). A logistic equation is fitted where the outcome is actually the main study exposure (i.e. surgical intervention); and an agreed list of covariates (these have already been identified and listed in appendix E) are introduced as potential confounders of the study outcome, namely subsequent re-dislocation. This list has been pre-specified based on clinical knowledge, expert consensus and existing literature. Propensity scores are used then to match each patient receiving surgery to comparable non-surgical controls using a 0.02 standard deviations caliper as demonstrated in previous simulation studies [2]. This is a standard method for minimising confounding by indication, which not only provides participants with balanced baseline characteristics in both surgical and non-surgical groups, but also eliminates surgical patients with no comparable controls [3].

This methodology is now widely used in pharmaco-epidemiology and drug safety, and has both strengths and limitations. The main advantages of PS-matching are:

1. Exclusion of non-comparable subjects (eg non-surgical participants with a very low propensity score who probably have some contraindication or are not fit for surgery, and therefore should not be compared to those who actually underwent surgical repair).
2. This method produces clearly comparable cohorts in terms of observed confounders, and this is highly visual and intuitive.

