APPENDIX E

Table of Expert Consensus List of Risk Factors.

Risk factors for re-dislocation after first dislocation	Risk factors for re- dislocation after surgery
Age	Age
Gender	Gender
UK Region	UK Region
Deprivation Scores	Deprivation Scores
Glenoid and / or Humeral Bone loss	Glenoid and / or Humeral Bone loss
Mechanism of injury	Number of dislocations pre-surgical repair
Rotator cuff tears	Time between first dislocation and surgery
Imaging findings	Anterior apprehension
Anterior apprehension	Occupation
Occupation	Sport type and level
Sport type and level	Operation type
Neurological injury	Laxity/Beighton Score
Laxity/Beighton Score	Insufficient physio / rehab after surgery
Insufficient physio / rehab after first dislocation	Time for return to sports
Young Rugby player under 20	Number of anchors used at surgery
Time at return to sports	Incorrect positioning of anchors
Post dislocation immobilisation	Not addressing capsular laxity at surgery
	Previous lower limb or back injury

This project was funded by the National Institute for Health Research Health Technology Assessment (project number 14/160/01).

The views and opinions expressed therein are those of the authors and do not necessarily reflect those of the HTA, NIHR, NHS or the Department of Health.

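### Section M credits propensity matching with dropping controls unfit for surgery, but the Appendix E covariates contain no general-health variable, so the specified score cannot reliably do this

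*Protocol*

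**What the plan says.** Section M lists two main advantages of propensity matching. The first is the exclusion of non-comparable subjects, with the example of "non-surgical participants with a very low propensity score who probably have some contraindication or are not fit for surgery".

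The same section says what goes into the score: "an agreed list of covariates (these have already been identified and listed in appendix E) are introduced as potential confounders". It adds: "This list has been pre-specified based on clinical knowledge, expert consensus and existing literature". Section L says of the same list: "We have already identified an expert consensus list of all potential confounders of interest (Appendix E").

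Appendix E is headed "Table of Expert Consensus List of Risk Factors". Its first column is titled "Risk factors for re-dislocation after first dislocation" and has 17 items; the second covers re-dislocation after surgery and has 18.

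Section K expects that some items will not be available in routine data and uses Work Package 1 to confirm which can be used. Section F foresees an updated analysis plan before Work Package 2. Sections L and M plan Rosenbaum bounds for unmeasured confounding, and Section M names the lack of matching on unobserved confounders as the method's main disadvantage.

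**The concern.** A propensity score can give a low value to patients unfit for surgery only if it contains something that carries fitness or contraindication. Appendix E was drawn up to answer what raises the risk of re-dislocation, not what decides who is operated on. If health status is absent from the score, an unfit control can look just like a fit patient with the same listed characteristics and be matched to an operated one.

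Where a reason for not operating also affects re-dislocation, this is the confounding by indication that the matched design is meant to reduce. Readers would also be told of a safeguard that the specified model does not supply.

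**Working it through.** **1. What the list contains.** The 35 entries (17 + 18, many shared) cover demographics, region, deprivation, bone loss, mechanism, imaging, apprehension, occupation, sport, laxity, rehabilitation and operative detail. The nearest to general health are rotator cuff tears, "Neurological injury" and, in the surgical column only, "Previous lower limb or back injury". Comorbidity, seizure disorder, BMI, smoking, alcohol and anaesthetic risk do not appear. Some entries, such as operation type and number of anchors, exist only in operated patients and so cannot predict who is operated on.

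**2. Other routes to exclusion.** The Section I exclusions concern linkage, length of follow-up, surgery after more than one dislocation, and rotator cuff or fracture surgery. None concerns fitness.

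**3. The plan's own figures.** Section G assumes two-year re-dislocation of 25% (control) and 20% (surgery): HR = ln(0.80)/ln(0.75) = 0.776. At 90% power and two-sided 5%, the Schoenfeld formula gives 652 events and the Freedman formula 659, against 656 stated. With exponential event and loss hazards and 10% loss, the mean event probability is 0.2140, and 656/0.2140 = 3065. The sample size reproduces and this point does not affect it.

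**4. Does matching remove unfit controls when fitness is not in the score?** This was simulated with assumed inputs: 10,449 patients, about 35% operated, 5% unfit and almost never operated, 1:1 matching with a caliper of 0.2 SD of the logit.

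| Link between fitness and listed covariates | Fitness in score? | Unfit, all controls | Unfit, matched controls |
|---|---|---|---|
| none | no | 7.6% | 8.2% |
| moderate | no | 8.0% | 7.4% |
| strong | no | 7.4% | 5.4% |
| none | yes | 7.5% | 0.1% |
| moderate | yes | 8.2% | 0.0% |
| strong | yes | 7.7% | 0.1% |

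The simulation printed a logistic-fit convergence warning. In one of the runs that included fitness, no unfit patient was operated. The runs show the mechanism and do not estimate it for this cohort.

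**5. Size and direction of the bias.** Let *q* be the unfit share of matched controls and *r* their re-dislocation risk relative to other controls. Both are assumptions, as is having no unfit patients in the surgical arm. Control risk = 0.25(1 − q) + 0.25·r·q. With no true effect, apparent HR = ln(0.75)/ln(1 − control risk). If surgery truly gives 20%, apparent HR = ln(0.80)/ln(1 − control risk).

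| q | r | Control risk | HR, no true effect | HR when truth is 0.776 |
|---|---|---|---|---|
| 5% | 1.5 | 0.2563 | 0.972 | 0.754 |
| 5% | 2 | 0.2625 | 0.945 | 0.733 |
| 10% | 2 | 0.2750 | 0.895 | 0.694 |
| 5% | 0.5 | 0.2438 | 1.030 | 0.799 |
| 10% | 0.5 | 0.2375 | 1.061 | 0.823 |
| 2% | 2 | 0.2550 | 0.977 | 0.758 |
| 2% | 0.5 | 0.2475 | 1.012 | 0.785 |
| 1% | 2 | 0.2525 | 0.989 | 0.767 |

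A harsher case (baseline risk 20%, hazard ratio of 3 for unfit against fit) gives 0.969 at a 2% share and 0.984 at 1%.

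**The case against.** The other side has several fair points.

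- **The sentence is general and hedged.** It describes advantages of the method, is given as an example and says only that such patients probably have a contraindication. That is right, and it is not a firm commitment. But it stands in this study's confounding plan as a reason to trust the matching.
- **Listed items may act as proxies.** Occupation, sport, deprivation and neurological injury may track fitness, and mechanism of injury could capture a dislocation caused by a seizure. This stands in part: the strong-correlation run removed some unfit controls but left 5.4%.
- **Unmeasured confounding is acknowledged.** Rosenbaum bounds are planned, and Section M limits its claim of comparability to observed confounders. The bounds say how strong a hidden bias must be to explain a result; they remove no unfit control. Diagnoses and admissions are also the kind of information that GP and hospital records hold.
- **Choosing covariates by their link to the outcome is defensible.** This stands. A factor that affects only the decision to operate is not a confounder, so additions should plausibly affect re-dislocation too.

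A reader might infer that the omission makes surgery look better. The documents do not support a direction: they give no re-dislocation risk for unfit patients, and since sport is a listed risk factor, less active patients could re-dislocate less. Nor do they support calling the list closed. It is pre-specified, but the updated plan after Work Package 1 could extend it, although nothing says that it will.

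**Conclusion.** The point holds as a mismatch between a stated benefit and the specified model. A low score from Appendix E does not identify patients unfit for surgery, and nothing else in the plan excludes them, so matching cannot be relied on to remove them.

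The size is uncertain and may be modest. With 5-10% of matched controls unfit and no true effect, the hazard ratio lies between about 0.89 and 0.97 at 1.5-2 times the risk, and between 1.03 and 1.06 at half the risk. At 1-2% unfit, which may be nearer the truth at ages 16-35, it moves by at most about 3%. These ranges rest on an assumed unfit share, an assumed relative risk and no unfit operated patients. The documents supply none of these.

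It should be corrected because the change is cheap and confounding by indication is the main threat that the design sets out to address. It does not show that the result would be wrong.

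**What to change.** In Sections L and M, or in the updated analysis plan due after Work Package 1, add to the propensity model covariates recorded in CPRD or HES before the first dislocation that plausibly affect both the decision to operate and re-dislocation. Candidates are comorbidity, seizure disorder and other recorded contraindications, with BMI, smoking and alcohol where recorded. The protocol does not itself tie these to re-dislocation, so the team should justify each one. Report their balance before and after matching.

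If they are not added, withdraw the statement that matching excludes patients unfit for surgery, and leave the matter to the acknowledged limitation and the Rosenbaum bounds.

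The cost is a short extra code list and a longer propensity model on data sources already planned; two years of CPRD data before the first dislocation code are already required. There may be slightly more unmatched surgical patients and a few more covariates to impute. Withdrawing the statement costs only a wording change.

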Population: 10,449 patients aged 16-35 years in CPRD with TASD and two years follow up.

WP1: Internal and external validation of shoulder dislocation coding and treatments within a routinely collected dataset (CPRD).

WP2: Propensity score-matched cohort study using linked CPRD and HES. All events and outcomes will be collected using a pre-agreed list of READ CODES (CPRD) and OPCS 4.7 CODES (HES).

Exclusions: Surgery after more than one dislocation; instability treated with a rotator cuff repair or fracture surgery.

Intervention: Surgical repair within 6 months of first time T ASD.

Control: non-surgical intervention.

Outcomes: Rate of re-dislocation, identified by codes in CPRD for 2 years after either treatment.

Sample size: 3065 with 656 expected total number of re-dislocations (90% power, 5% significance).

Statistical analysis: Propensity scores, Cox regression modelling and Rosenbaum bounds sensitivity analysis for *Surgical versus non-surgical intervention on re-dislocation*. Multiple imputation methods, survival models and fractional polynomials for *Predictors of recurrent dislocations*.

C. Objectives, Specific Aims and Rationale

Aim 1. To study the association between surgical treatment (compared to no surgery) and recurrence rates following a first episode of traumatic anterior shoulder dislocation (T ASD) amongst young adults. **Aim 2.** To identify clinical predictors of further recurrent dislocations in young adults with traumatic anterior shoulder dislocation stratified by surgery and no surgery.

Objectives: Following the HTA commissioning brief, we plan to use routinely collected observational datasets (Clinical Practice Research Datalink (CPRD) and Hospital Episodes Statistics (HES)) to answer the research questions above. The size of routinely collected data in UK primary care (CPRD) and secondary care (HES) offers rapid observational data to uncertainties about treatments in an affordable and generalisable manner. We have planned a propensity score-matched cohort study, with the intention to minimise confounding. Propensity score matching is considered one of the best methods available to approximate to any results obtained from randomised controlled trials. To ensure further value for money and to confirm the ability of these datasets to answer this very specific commissioned question, we plan a two stage approach through Work Packages 1 and 2.

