Using data from a Cochrane systematic review comparing surgical to non-surgical treatment for acute T ASD [6]; from the pooled results 3/58 patients in the surgical arm had subsequent further surgery (5.17%) compared to 17/61 in the non-surgical arm (27.9%) at a minimum follow up of 2-years (Risk Ratio 0.22, 95% CI 0.08 to 0.64). The large effect size is set in the context of the pooled results of 3 RCTs with uncertainty around the true size of the effect outside of a clinical trial setting in routine general practice. Conservatively, we would look to detect a smaller difference in subsequent surgery within 2-years of 25% in the non-surgical group, compared to 20% in the surgical group (an absolute difference of 5%). A 2-sided log rank test for equality of survival curves, with 90% power at 5% significance level (alpha), where outcome is time to re-dislocation, with an anticipated 25% re-dislocation rate in the non-surgical control group compared to a 20% in the surgical group (equivalent to a hazard ratio of 0.78), allowing for 10% loss to follow up and assuming equal group sizes, we require a total sample size of 3065 with 656 expected total of re-dislocations. There are 26,534 patients in CPRD with recurrent anterior shoulder dislocations, and at least 10,449 of these patients will be aged 16-35 years with T ASD [7]. The study will therefore be adequately powered. ***See flow diagram in appendix for estimation of numbers.***

H. Data Linkage Required (if applicable)

Data linkage and data management for our proposed study involves 2 different data sources (CPRD and HES). They need to be linked to answer the aims of WP2 as stated above. We have therefore included co-applicants with extensive experience in the use of linked datasets. The data management needed to produce a final working dataset will be carried out by a senior data manager at Oxford with expertise in such procedures. Under supervision from the application team, the data manager will develop ad-hoc code in Python and SQL to produce a dataset that can be analysed using standard statistical packages such as Stata.

I. Study Population

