Matched surgical patients and their non-surgical controls will then be included in a Cox regression survival model to describe the association between receipt of surgery and time to subsequent dislocation within 2-years. The model is stratified on matched sets, to allow for the correlation between matched pairs of surgical patients and controls. As clustering exists within the data (patients nested within GP practices), a multilevel survival model will be fitted by extending the Cox regression model to include a frailty term with a Gaussian distribution[8]. This will allow adjustment for evidence of unexplained variation across GP practices. To assess the potential effect of unmeasured confounders we will conduct a Rosenbaum bounds sensitivity analysis[9]. This provides an estimate of the magnitude of hidden bias that would have to be present to explain the associations actually observed. The proportional hazards assumption will be assessed using Schoenfeld's residuals. Kaplan-Meier plots will be used to estimate the probability of survival up to 2-years in surgical and non-surgical groups.

Identifying predictors of recurrent dislocations

Using the CPRD-HES linked dataset we will develop a prediction model to identify patients at increased risk of subsequent re-dislocation. Potential risk factors will include all those described above. The cumulative effect of missing data in several variables often leads to exclusion of a substantial proportion of the original sample, causing a loss of precision and power. To overcome this bias we will use multiple imputation methods, which allows for the uncertainty about missing data by creating several plausible imputed datasets and appropriately combining their results [10, 11].

Survival models (Cox regression) will be used to identify risk factors associated with time to re-dislocation. Backward selection methods will be used to identify risk factors and shrinkage methods applied to adjust for over fitting. Continuous predictors will be examined using fractional polynomials and clinically plausible interaction terms will be tested for inclusion (specifically whether the predictors differ in the surgical and non-surgical intervention groups). For internal validation of the model we will use a combination of multiple imputation and bootstrapping[12-14].

Performance of the model will be assessed in terms of calibration and discrimination[11, 23]

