The main disadvantage (when compared to RCTs) is the lack of adjustment/matching for unobserved confounders. To measure the impact of such unobserved confounding we will use the Rosenbaum boundaries simulation, where one tests the robustness of the estimated effect by introducing a fake confounder. This simulation exercise measures the strength of association between such confounder and the study exposure and outcome that would account for the observed relationship, therefore giving an estimate of the existing risk of residual confounding explaining the findings.

N. Plan for addressing missing data

The handling of missing data is a key issue in routinely collected data analyses. Although no missing is expected for the study exposure or outcomes, it is indeed likely that data will be missing for some of the confounders in our study.

This project was funded by the National Institute for Health Research Health Technology Assessment (project number 14/160/01).

The views and opinions expressed therein are those of the authors and do not necessarily reflect those of the HTA, NIHR, NHS or the Department of Health.

We will impute missing covariates using multiple imputation by chained equations (MICE) methods. We will use the ICE procedure (Imputation by Chained Equations) in Stata, including all predictor variables in the multiple imputation process, together with the outcome variable and length of follow up time on the log scale as this carries information about missing values of the predictors.

O. Limitations of the study design, data sources and analytical methods

The limitations have all been considered and addressed in the other sections. The study has also been designed deliberately in two stages to ensure data validation is undertaken in stage 1 and that the research questions can be answered before progressing to the full observational study.

P. Patient or user group involvement (if applicable)

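### The imputation model listed in Section N has no treatment interactions and no by-group step, so for incomplete predictors it shrinks the surgical versus non-surgical differences that Aim 2 tests

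*Protocol*

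**What the plan says.** Section N expects gaps in the covariates: "it is indeed likely that data will be missing for some of the confounders in our study". It then names the method, "We will impute missing covariates using multiple imputation by chained equations (MICE) methods", and what goes into it: "including all predictor variables in the multiple imputation process, together with the outcome variable and length of follow up time on the log scale". Neither that section nor any other adds an interaction with surgery or a by-group step to the imputation.

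Aim 2 in Section C is "To identify clinical predictors of further recurrent dislocations in young adults with traumatic anterior shoulder dislocation stratified by surgery and no surgery". In Section L, the prediction model is a Cox regression with backward selection in which interaction terms are tested, "specifically whether the predictors differ in the surgical and non-surgical intervention groups".

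Appendix E gives two risk-factor lists, one for re-dislocation after a first dislocation and one for re-dislocation after surgery. They overlap (age, gender, region, deprivation, occupation, sport and others). The surgical list also has entries with no meaning for an unoperated patient, such as operation type, number and placement of anchors, and time from dislocation to surgery.

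**The concern.** An imputation model should contain the associations that the analysis model will test. Here the analysis asks whether a predictor's effect depends on surgery, while the listed imputation model allows each incomplete predictor only one association with the outcome, common to both groups. Observed records keep any true difference. Imputed records show an averaged association in both groups. The combined estimate lies between the two, and group-specific effects are drawn towards each other.

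The error has a known direction: towards concluding that the same predictors apply with and without surgery. Backward selection would tend to add to this, since an attenuated interaction is easier to drop, although that step was not simulated.

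**Working it through.** **The plan's own figures.** The protocol states no figure for the imputation. Its design figures, some of which set the simulations, can be reproduced.
- Rates of 25% and 20% give HR = ln 0.80 / ln 0.75 = 0.7757.
- Events by Schoenfeld: 4 × (1.960 + 1.282)² / (ln 0.7757)² = 652. Freedman's formula gives 659. The protocol has 656.
- With exponential event times and 10% exponential loss over two years, the event probabilities are 0.2379 and 0.1902, mean 0.2140. 3065 × 0.21404 = 656.

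**Expected shrinkage.** Let θ be the true log interaction (log ratio of hazard ratios) and m the share of the predictor missing completely at random. Observed records contribute θ and imputed records about 0, so the estimate is roughly (1 − m) × θ.

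**Simulation A (assumed values).** 8,000 patients, about 35% operated (the share assumed in Appendix B), surgery HR 0.78, about 20–25% events by two years, one binary predictor with missing values and one complete continuous covariate. True ratio of hazard ratios 0.60, so θ = ln 0.60 = −0.51. 60 replicates, 3 imputations, exponential model.

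| Missing | (1 − m) × θ | As listed | Plus surgery main effect | By group |
|---|---|---|---|---|
| 10% | −0.46 | −0.46 | −0.46 | −0.51 |
| 30% | −0.36 | −0.35 | −0.35 | −0.52 |
| 50% | −0.26 | −0.25 | −0.26 | −0.53 |

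Share retained as listed: 0.46/0.51 = 90%, 0.35/0.51 = 69%, 0.25/0.51 = 49%.

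**Simulation B (assumed values).** 3,065 patients, Cox model, binary predictor with prevalence 40%, hazard ratio 2.0 without surgery and 1.0 with surgery, so θ = ln 0.50 = −0.693. 150 replicates, 3 imputations. The last column used a joint model with surgery, surgery × event and surgery × log time, which is equivalent to imputing by group in this one-predictor set-up.

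| Missing | As listed: ratio of HRs | Share of θ kept | Share kept, plus surgery main effect | Share kept, by group |
|---|---|---|---|---|
| 20% | 0.58 | 79% | 79% | 101% |
| 40% | 0.67 | 59% | 59% | 102% |
| 60% | 0.78 | 37% | 38% | 101% |

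With no true interaction and 40% missing (40 replicates), every method gave an estimate near zero (−0.02 to −0.03; full data −0.04). The listed model therefore hides real differences and does not create false ones.

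Both simulations give the same pattern. The loss follows the missing share, a surgery main effect does not repair it, and imputing by group does.

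**The case against.** The strongest reply is that Section N names what the imputation includes and does not say that nothing else will be added, or that one run will cover both groups. By-group running and interaction terms are details often left to an analysis plan, and Section F promises an updated plan before the main study. Aim 2 is itself stratified, and Appendix E's two lists hardly fit a single run. This shows that by-group imputation is compatible with the protocol, and it is why the fix is easy. It does not remove the point: Section N goes as far as listing the model's contents, and a team following that list would have a model that does not fit the stated interaction analysis.

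Second, the sizes rest on assumptions. The protocol gives no missing share and no predictor effects. Sections F and K restrict the main study to factors that the validation stage finds reliably recorded, which argues against the highest missing shares. At 10% missing the loss is modest (−0.51 to −0.46). This stands.

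Third, a reader might infer that surgery is absent from the imputation, so that imputed confounders stay unbalanced and the primary matched hazard ratio is biased. The documents do not support this.
- Surgery enters the Section L prediction model and can be read as one of the predictors.
- The Section N sentence that names the exposure says only that no missing values are expected in exposure or outcomes. The outcome is treated the same way there, yet is explicitly in the imputation model.
- The Technical Summary attaches multiple imputation to the predictor analysis. Section N does mention confounders, so this last item is ambiguous.

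One binary confounder (HR 2.0, log odds ratio 1.0 for surgery) was checked with covariate adjustment in place of matching. A surgery main effect alone gave surgical hazard ratios of 0.774, 0.784 and 0.777 at 20%, 40% and 60% missing, against 0.773, 0.784 and 0.771 with full data. Inclusion as a predictor would therefore settle the matter in that setting.

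**Conclusion.** The point holds for Aim 2. Followed as listed, Section N attenuates between-group differences for predictors with missing values, by about 10%, 30% and 50% of the log interaction at 10%, 30% and 50% missing. Reading surgery into the predictor list leaves this unchanged.

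The figures assume a single binary predictor missing completely at random and chosen effect sizes. The direction follows from the form of the model; the size in this study depends on a missing share that is not yet known. Predictors recorded for everyone, for example age and gender if complete, are not attenuated in this way. Neither simulation included the pre-surgery interval that Section L handles as time-varying exposure.

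For the primary matched hazard ratio there is only a wording gap to close. No bias is established.

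**What to change.** State in Section N that the chained-equations imputation is run separately in the surgical and non-surgical groups, each with its own Appendix E predictor list (as far as the validation stage supports it), the outcome and log follow-up time. The imputed groups are then stacked for analysis. Where a group is too sparse for a covariate, impute jointly with surgery and its interactions with the event indicator and the covariates in the model. The joint form checked above also carried surgery by log follow-up time.

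As a clarification, add that surgery is in any imputation model whose covariates feed the propensity score, where "A logistic equation is fitted where the outcome is actually the main study exposure (i.e. surgical intervention").

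This needs no new data, only a short addition to Section N and a change to the imputation command. The statistical cost is slightly wider standard errors for imputed covariates, because each group's model uses fewer patients. Since groups would be split by eventual surgery, the team should confirm that the split sits well with the time-varying exposure in Section L; that was not tested here.
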